## VERSION HISTORY

### Version 1, Version Date 07/31/2021

Initial submission of the protocol.

Version	Date
1	07/31/2021

## PROTOCOL SUMMARY

Title	Evaluating Impact of Near Infrared Autofluorescence (NIRAF) Detection for Identifying Parathyroid Glands during Parathyroidectomy
Principal Investigator	[name]
Study Population	Parathyroidectomy patients
Primary Objectives	The specific aim of this study is to determine if PTeye is beneficial or not for (i) intraoperative identification of parathyroid tissues, (ii) improving efficiency of parathyroid surgeries, and (iii) minimizing risk of postsurgical complications.
Study Design	Double-arm, open-label
Study Intervention	PTeye
Number of Subjects	N = 160. Each investigator will enroll 40 subjects to the PTeye group and 40 subjects to the control group.
Estimated Time to Complete Enrollment:	Approximately 2 years

# 1 BACKGROUND

## Parathyroid Surgery

Inability of the surgeon to identify or localize the diseased PG can occur in 5 – 10% of cases resulting in failed parathyroidectomies (1, 2). As a result, persistent hyperparathyroidism can occur in these patients resulting in unnecessary repeat surgeries that may be associated with increased morbidity and costs (3, 4). Ultrasound imaging, 99mTechnetium-sestamibi scintigraphy, and computed tomography (CT) have so far demonstrated variable efficacy in preoperative localization of diseased PGs (5, 6) and may not always correlate well with the surgical field of view as observed intraoperatively. Consequently, most surgeons rely on visual identification of PGs during surgery, whereby the accuracy of PG identification is eventually determined by her/his surgical skill and experience (7, 8). When in doubt, a surgeon routinely confirms the identity of PG tissue intraoperatively by sending the specimen for frozen section analysis that typically requires a wait time of 20–30 minutes per sample (9) and has additional costs.

By easily being able to distinguish parathyroid from other tissues intraoperatively, postsurgical complications and associated costs may be reduced. The unique discovery of near infrared autofluorescence (NIRAF) in parathyroid tissues demonstrated that optical modalities that detect NIRAF can be utilized for non-invasive and label-free identification of parathyroid tissues with an accuracy as high as 97%.(10, 11) Since then, several research groups have explored the feasibility of localizing parathyroid glands using NIRAF detection with reasonable success, resulting in FDA approval for this optical technique (12). In this study, we plan to evaluate whether an FDA-approved device called 'PTeye' (AiBiomed, Santa Barbara, CA) is beneficial or not, for the surgeon and patient during parathyroid operations. The results of such a study will help us to understand and assess the true impact of optical modalities such as PTeye on (i) improving the quality and efficiency of parathyroid surgeries and (ii) minimizing risk of postsurgical complications and related expenses.

## Animal Studies and Previous Human Studies

Modalities that rely on NIRAF detection for label-free parathyroid identification have been successfully validated in several studies (13-16). FDA approval for this application was recently granted to Fluobeam (a commercially available imaging system) and PTeye (a commercial fiber probe-based system) in 2018 (12). Certain outcome studies have reported that imaging-based systems for NIRAF detection such as the PDE Neo II system was able to reduce the number of frozen sections required during parathyroid procedures (15). However, other studies have reported that they observed no benefit from imaging-based systems in parathyroid localization (17). In a recent study, Thomas et al. demonstrated that a fiber probe-based system – the PTeye – was more sensitive in parathyroid identification compared to the imaging-based system by PDE Neo II (18). To date, there has been no studies that determine the impact of a fiber probe-based system (i.e. PTeye) during parathyroid surgeries in minimizing a number of frozen sections obtained intraoperatively or postsurgical complications.

## Known Risks and Potential Benefits

The proposed study is designed to collect NIRAF measurements from neck tissues with a commercial device called PTeye during a parathyroidectomy. The device that will be used for NIRAF measurements is an FDA-approved device.

Each PTeye measurement takes less than 2 seconds, with the whole set of measurements not adding more than 5 minutes to the surgical procedure. Thus, there is a minimal increase of risk of surgery due to the potential five extra minutes of anesthesia time associated with the study. In addition, the participating surgeon will evaluate the eligibility of the patient based on his or her medical condition. Patients with high anesthetic risks will not be asked to participate in the study.

Since the power of near infrared light from PTeye will be extremely low, no side effects should be introduced to the patient.

There should not be any discomforts, inconveniences, and/or risk resulting from this study.

The study should not increase the risk of infection as a disposable sterile probe is used for each patient.

The PTeye device used in this study has been FDA-approved. The FDA approval is granted based on the caveat that necessary precautionary measures will be taken by the surgeon to minimize the probable risks (as listed in the device brochure). The PTeye may be associated with unknown/unforeseen risks as with any other FDA-approved medical devices used during surgical procedures.

## **2 HYPOTHESIS, OBJECTIVES, AND ENDPOINTS**

The goal of this study is to assess whether using PTeye – a NIRAF detection modality – can improve patient outcomes and reduce healthcare associated costs after parathyroid surgeries.

By being able to quickly and definitively locate parathyroid glands while in the operating room, the duration of surgical procedure could be further reduced. In addition, the number of frozen section biopsy and associated costs can be minimized. Furthermore, repeat surgeries as a result of missing a diseased parathyroid gland at the time of the initial parathyroidectomy for hyperparathyroidism could potentially be avoided.

### **2.1 Primary Objective**

The specific aim of this study is to determine if PTeye is beneficial or not for (i) intraoperative identification of parathyroid tissues, (ii) improving efficiency of parathyroid surgeries, and (iii) minimizing risk of postsurgical complications.

### **2.2 Primary Outcome Measures**

#### **2.2.1 Persistent hyperparathyroidism (Immediate)**

Failure of intra-operative parathyroid hormone (PTH) to normalize (defined as failure of PTH to drop > 50% of its baseline value at final intra-operative PTH assay and/or failure of PTH to drop < 65 pg/ml or 6.9 pmol/L). [Time Frame: During parathyroidectomy (PTx) procedure]

#### **2.2.2 Persistent hyperparathyroidism or hypercalcemia (transient)**

Elevated blood calcium levels (total blood calcium level > 10.5 mg/dL or 2.6 mmol/L) with/without elevated parathyroid hormone (PTH) (serum intact PTH > 65 pg/ml or 6.9 pmol/L) at first postoperative visit. [Time Frame: 5-14 days after PTx procedure]

### **2.2.3 Persistent hyperparathyroidism or hypercalcemia (failed parathyroidectomy)**

If blood calcium with/without parathyroid hormone (PTH) has not normalized at 1st post-operative visit, calcium and/or PTH is subsequently measured as necessary. Patient is defined to have a failed parathyroidectomy if hypercalcemia/hyperparathyroidism (defined as total blood calcium level > 10.5 mg/dL or 2.6 mmol/L, with/without elevated serum intact PTH > 65 pg/ml or 6.9 pmol/L) persists at or after the 6th postoperative month. [Time Frame: 6 months after PTx procedure]

## **2.3 Secondary Outcome Measures**

### **2.3.1 Overall number of parathyroid glands identified**

Overall number of parathyroid glands identified (Experimental Group: Glands identified with naked eye + NIRAF; Control Group: Glands identified with naked eye) [Time Frame: Immediate. During PTx procedure.]

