### **2.3.3 Number of frozen sections sent for analysis**

Number of frozen sections sent for analysis during the procedure to confirm potential parathyroid tissue [Time Frame: Immediate. During PTx procedure.]

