#### **2.3.11 Number of 'false positive' tissues excised by surgeon**

Number of tissues that were excised by surgeon assumed to be parathyroid tissue, but is later validated as nonparathyroid tissue (false positive) by histology [Time Frame: Immediate to 10 days after PTx procedure.]

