## 6 STATISTICAL CONSIDERATIONS

Benmiloud et al. studied the impact of NIRAF-based identification of parathyroid glands which comprised of a group of 93 patients where NIRAF was used by a surgeon for parathyroid identification and a control group of 153 patients where NIRAF was not used (19). Their study reported that mean parathyroid glands identified by surgeon with NIRAF imaging was significantly higher at  $3.1 \pm 0.9$ , while that of same surgeon without NIRAF imaging was  $2.6 \pm 0.1$  ( $p=0.0001$ ). Based on this data (mean difference: 0.5 and standard deviation: 1.0), it was determined that in order to observe a statistically significant difference (i.e. for an expected mean difference: 0.7 and expected standard deviation: 1.0), 33 patients would be required per group (for a 95% powered study). Since this study may involve patient follow-up for data up to 6 months after surgery, we will thus assume an approximate data attrition rate of 20%, thus requiring a recruitment of 40 patients per group. Therefore, a total of 80 patients (study and control arm) should be recruited per surgeon for this study at this study site.

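### Does the gland count in 2.3.1 need a written rule for tissue that histology later shows is not parathyroid?

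*Combined protocol and SAP*

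**What the plan says.** Section 2.3.1, a secondary outcome timed during the procedure, counts glands as follows: "Experimental Group: Glands identified with naked eye + NIRAF; Control Group: Glands identified with naked eye". It names no confirming standard. Section 2.3.2, the count of glands found by NIRAF alone, names none either.

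Section 2.3.11 counts excised tissue "assumed to be parathyroid tissue, but is later validated as nonparathyroid tissue (false positive) by histology", with the window "Time Frame: Immediate to 10 days after PTx procedure". It is not limited to one arm. The Day of Parathyroidectomy list under section 4.9 collects frozen-section and permanent histology reports on everything excised.

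Frozen section appears in three places. Section 1 describes usual practice: "When in doubt, a surgeon routinely confirms the identity of PG tissue intraoperatively by sending the specimen for frozen section analysis". Section 2.3.3 counts its use: "Number of frozen sections sent for analysis during the procedure to confirm potential parathyroid tissue". Section 2 hopes that, with the device, "the number of frozen section biopsy and associated costs can be minimized".

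Section 6 bases the sample size on gland counts alone, citing a study in which "mean parathyroid glands identified by surgeon with NIRAF imaging was significantly higher at" 3.1, against 2.6 without imaging. The Protocol Summary describes an open-label trial with N = 160, 40 per arm for each investigator.

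**The concern.** The device is meant to detect tissue, so a count that does not separate true from false detections cannot show by itself that more parathyroid tissue was found. The 2.3.1 window closes before permanent histology is available, and 2.3.11 shows that the plan expects some calls to be wrong. If the intraoperative count stands, one refuted structure is both a gland identified and a false positive.

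The trial is open-label and only one arm has the device, so wrong calls need not balance. Extra wrong calls with PTeye would inflate the difference. Wrong naked-eye calls that PTeye prevents would hide a gain. With the rule unwritten, the gross count (as called in theatre) or the net count (less refuted tissue) could be picked after the data are seen, for the one outcome that sets the sample size.

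**Working it through.** **The plan's own figure.** Section 6 states 33 per group for a difference of 0.7, SD 1.0 and 95% power. With n = 2(z₁₋α/₂ + z_power)²σ²/δ² and two-sided 5%:

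- 95% power: 2(1.960 + 1.645)²/0.49 = 53.04, so 54 per group.
- 80% power: 2(1.960 + 0.842)²/0.49 = 32.04, so 33 per group.

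The stated 33 thus matches 80% power, not 95%. That is a separate matter, and nothing below depends on it.

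**How far the two counts can differ.** Suppose 2.3.1 is recorded as the gross count. As far as excised tissue goes, a patient's net count then lies between (2.3.1 minus 2.3.11) and 2.3.1. If it is recorded as the net count, the gross count lies between 2.3.1 and (2.3.1 plus 2.3.11). Either way the gap is at most the 2.3.11 count, which is itself a reported outcome.

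**Inputs for the illustration.**

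- SD 1.0 and true difference 0.7: section 6.
- 40 per arm (one surgeon): section 6 and the Protocol Summary. 80 per arm: 160/2, assuming two surgeons are pooled. No attrition is applied.
- Two-sample t-test at two-sided 5%: assumed, because section 6 names no test or alpha.
- Imbalance of 0.05 to 0.10 refuted structures per patient: pure assumption. At 40 per arm this is 0.05 × 40 = 2 to 0.10 × 40 = 4 structures, or 0.05/0.7 = 7% to 0.10/0.7 = 14% of the planned difference.

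The 97% in section 1 cannot anchor this range. It is a best-case overall accuracy, so its complement also includes missed parathyroid tissue. The 3.1 glands in section 6 come from an imaging study whose title (reference 19) places it in total thyroidectomy, not probe-guided parathyroidectomy.

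**Formula.** Noncentrality = δ/(σ√(2/n)), with 2n − 2 degrees of freedom.

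| Case | 40 per arm (√(2/40) = 0.2236; critical t 1.991) | 80 per arm (√(2/80) = 0.1581; critical t 1.975) |
|---|---|---|
| No benefit, excess 0.05 with PTeye | 0.224, rejects 5.6% | 0.316, rejects 6.1% |
| No benefit, excess 0.10 with PTeye | 0.447, rejects 7.3% | 0.632, rejects 9.6% |
| True 0.7, no imbalance | 3.130, power 87.1% | 4.427, power 99.3% |
| True 0.7, excess 0.05 in control (0.65 seen) | 2.907, power 81.9% | 4.111, power 98.3% |
| True 0.7, excess 0.10 in control (0.60 seen) | 2.683, power 75.5% | 3.795, power 96.5% |

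**What a net count would do.** Histology reaches only tissue that was sampled. Suppose 0.10 wrong calls per patient in each arm, all checked in control but only half with PTeye.

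- Gross count: 0.10 − 0.10 = 0, no bias.
- Net count: 0.10 × (1 − 0.5) − 0.10 × (1 − 1) = 0.05, a spurious difference in favour of PTeye, rejecting 5.6% of the time at 40 per arm.

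Unequal checking is plausible, because fewer frozen sections is one of the hoped-for effects of the device.

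**The case for a change.** The strongest case for a change is that two analysts could follow this protocol and build different 2.3.1 datasets. The noun *gland* does not settle the matter, because 2.3.1 closes before permanent histology is back and a confident wrong call need not go to frozen section. Intraoperative identification is the first listed aim, the count sets the sample size, and a rule would cost a sentence and use histology already collected.

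Much of this stands. The rule is unwritten, the same gap affects 2.3.2, and an analyst will have to say which count is being reported. What does not follow is that the plan gives a wrong result. An intraoperative count beside a histology-based false-positive count is a coherent pair: what was called, and which excised calls were wrong. A structure appearing in both is no error in itself. The worry about choosing after seeing the data applies to every outcome here, since section 6 contains only a sample-size paragraph. Nor is the obvious remedy a clear gain. Netting corrects excised tissue only, leaves glands in place unverified, and can create a difference where the gross count has none.

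**Conclusion.** No change to the plan follows. This is a missing detail that analysts can fill sensibly: use one rule in both arms, say which count is reported, and read it beside 2.3.11. The ordinary meaning of a parathyroid gland already excludes refuted tissue. On the other reading, wrong excisions remain visible in both arms, and for excised tissue the two counts cannot differ by more than the 2.3.11 count.

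Under the assumed imbalance of 0.05 to 0.10 per patient, the effect is modest: 5.6% to 7.3% rejection against a nominal 5% at 40 per arm, and 6.1% to 9.6% at 80. In the other direction, power falls from 87.1% to between 81.9% and 75.5% at 40 per arm, and hardly moves at 80. These figures rest on an assumed test, SD 1.0, no attrition and an imbalance for which the documents give neither size nor direction. A markedly larger imbalance would matter more, but nothing in the documents points to one. The three primary PTH and calcium outcomes do not use the gland count. The choice between gross and net is a fair trade-off, and neither count is free of bias.

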### **2.3.2 Number of parathyroid glands identified with NIRAF**

Number of parathyroid glands identified with NIRAF, which was not seen with surgeon's naked eye [Time Frame: Immediate. During PTx procedure.]

### **2.3.3 Number of frozen sections sent for analysis**

Number of frozen sections sent for analysis during the procedure to confirm potential parathyroid tissue [Time Frame: Immediate. During PTx procedure.]

### **2.3.4 Number of diseased parathyroid glands identified versus preoperatively localized glands**

Number of diseased parathyroid glands identified intra-operatively versus glands localized preoperatively using sestamibi, CT or ultrasound [Time Frame: Preoperative to immediate during PTx procedure.]

### **2.3.5 Number of intra-operative parathyroid hormone (PTH) assays sent**

Number of intra-operative parathyroid hormone assays sent during the procedure [Time Frame: Immediate. During PTx procedure.]

### **2.3.6 Duration taken to identify first parathyroid gland**

Duration taken to identify 1st parathyroid gland in PTx procedure – timed from skin incision to finding PG. [Time Frame: Immediate. During PTx procedure.]

### **2.3.7 Duration taken to identify last parathyroid gland**

Duration taken to identify last parathyroid gland in PTx procedure – timed from skin

incision to finding the last PG.[Time Frame: Immediate. During PTx procedure.]

#### **2.3.8 Duration of parathyroidectomy (PTx) procedure**

Duration of PTx procedure – timed from skin incision until the surgeon notifies the anesthesia team to awaken the patient [Time Frame: Immediate. During PTx procedure.]

#### **2.3.9 Duration taken for intraoperative parathyroid hormone (PTH) to normalize**

Time taken for PTH to attain cure criteria or normalize - timed from skin incision until the PTH levels drops > 50% of its baseline value and/or PTH drops < 65 pg/ml or 6.9 pmol/L. [Time Frame: Immediate. During PTx procedure.]

#### **2.3.10 Number of nights spent in the hospital after parathyroidectomy**

Number of nights spent for postoperative recovery in the hospital after the surgical procedure. [Time Frame: 0-72 hours after PTx procedure.]

#### **2.3.11 Number of 'false positive' tissues excised by surgeon**

Number of tissues that were excised by surgeon assumed to be parathyroid tissue, but is later validated as nonparathyroid tissue (false positive) by histology [Time Frame: Immediate to 10 days after PTx procedure.]

#### **2.3.12 Number of doctor visits/emergency department visits or hospital admissions**

Number of doctor visits/emergency department visits or hospital admissions due to persistent hypercalcemia and/or associated symptoms after parathyroidectomy procedure [Time Frame: Up to 6 months after PTx procedure.]

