## **Follow-Up Visits**

Patients will be followed for six months following parathyroidectomy. The visits will be within 5-14 days after surgery and at 6 months after surgery. The following procedures will be performed at the follow-up visit(s):

- Physical examination
- Vital signs
- Blood chemistry assessment of serum calcium, ionized calcium, parathyroid hormone (PTH) levels, and 25-OH vitamin D levels
- Concomitant medications
- History of visits to the Emergency room, hospitalization, or repeat surgery due to high calcium levels

- Documentation of postsurgical complications

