### **5.2.3 Routine Reporting Procedures for AEs**

#### *Expedited Reporting Procedures for SAEs, SARs, UPIRSOs and DLTs.*

Since this is an investigator-initiated study, the principal investigator, also referred to as the sponsor-investigator, is responsible for reporting serious adverse events (SAEs) to any regulatory agency and to the sponsor-investigator's IRB. Regardless of expectedness or causality, all SAEs (including serious pretreatment events) must also be reported to the DSMC as soon as possible, but no later than five calendar days of the sponsor-investigator's observation or awareness of the event.

Signs or symptoms reported as adverse events will be graded and recorded by the investigator, according to the CTCAE. When possible, signs and symptoms indicating a common underlying pathology should be noted as one comprehensive event.

The investigator will assess all adverse events and determine reporting requirements to the MCWCC Data and Safety Monitoring Committee (DSMC) and MCW's Institutional Review Board, and, when the study is conducted under an Investigational New Drug Application (IND), to the Food and Drug Administration (FDA), if it meets the FDA reporting criteria. The investigator will report SAEs to any regulatory agency and to the sponsor-investigator's IRB.

All adverse events, whether or not unexpected, and whether or not considered to be associated with the use of the study drug, will be entered into OnCore®.

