## **8.6 Study Record Retention**

The duration of the study is expected to be approximately two years and will depend on patient availability. The data acquired from this study will be preserved indefinitely, as it may influence the future development of the entire research project. However, the data will not be accessible to anyone other than the participants of this study. All original paper records, record sheets, preoperative and postoperative lab investigations, drug/medication history, post-surgical medical history, histopathological diagnoses of the investigated tissue samples, will be collectively retained by the PI or Key Study Personnel. The data of this study will be stored in a password protected computer, and only users with permission from the PI can access the data base.

The PI at each participating site is required to prepare and maintain adequate records of the disposition of study materials and case histories that record all observations and other data pertinent to the investigation on each individual administered the materials in the investigation. Case histories include the case report forms and supporting data including, for example, signed and dated consent forms. The case history for each individual shall document that informed consent was obtained prior to participation in the study.

Study documentation includes all data entry forms, data correction forms or queries, source documents, Sponsor-Investigator correspondence, monitoring logs/letters, and regulatory documents (e.g., protocol and amendments, IRB correspondence and approval, signed participant consent forms).

Source documents include all recordings of observations or notations and all reports and records necessary for the evaluation and reconstruction of the clinical research study.

The principal investigator is required to prepare and maintain adequate and accurate case histories that record all observations and other data pertinent to the investigation on each individual administered the investigational drug or employed as a control in the investigation. Case histories include the case report forms and supporting data including, for example, signed and dated consent forms and medical records including, for example, progress notes of the physician, the individual's hospital chart(s), and the nurses' notes. The case history for each individual shall document that informed consent was obtained prior to participation in the study.

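### Outcome 2.3.12 counts doctor visits and contacts for associated symptoms, but the follow-up history item names neither, so a site following the list would undercount it

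*Combined protocol and SAP*

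**What the plan says.** Section 2.3.12 of the combined protocol and SAP sets as a secondary outcome the "Number of doctor visits/emergency department visits or hospital admissions due to persistent hypercalcemia and/or associated symptoms after parathyroidectomy procedure", with "Time Frame: Up to 6 months after PTx procedure".

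The Follow-Up Visits list states when patients are seen: "The visits will be within 5-14 days after surgery and at 6 months after surgery". Its one item on use of health care reads "History of visits to the Emergency room, hospitalization, or repeat surgery due to high calcium levels". The same list also has "Documentation of postsurgical complications", with no definition of a complication and no count of contacts.

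Repeat surgery, which the history item includes, is the subject of a separate outcome, 2.3.13.

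**The concern.** The history item is the one place where the protocol tells sites to ask about health-care use after surgery, and it is narrower than the outcome it serves. Consider a patient seen several times in a doctor's office for persistent hypercalcemia and never sent to an emergency department or admitted. A coordinator who asks only the listed question would record nothing for that patient, although every one of those visits belongs in 2.3.12.

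The opening of section 2 gives lower health-care costs as part of the study's goal, and 2.3.12 is one of the outcomes that bears on it. If sites fill the gap from charts on their own initiative, capture could vary between patients. The Protocol Summary describes the trial as open-label, so it could also vary between arms. That is a possibility, not something the documents show.

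**Working it through.** The plan gives no figure on this point, so the check compares the outcome with each place where its data could be collected.

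**Step 1. Break the outcome into its parts.** Section 2.3.12 names three contact types and two reasons, which gives 3 × 2 = 6 combinations. The table shows which of them the Follow-Up Visits history item names.

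| Contact type in 2.3.12 | For persistent hypercalcemia | For associated symptoms |
|---|---|---|
| Doctor visit | not named | not named |
| Emergency department visit | named | not named |
| Hospital admission | named | not named |

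The item names 2 of the 6. This counts categories, not events, so it does not mean that two thirds of contacts are missed.

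**Step 2. State what the listed item yields.** Let D, E and H be the numbers of doctor visits, emergency department visits and admissions, with subscript c for hypercalcemia and s for associated symptoms only.

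- Outcome as defined: D_c + D_s + E_c + E_s + H_c + H_s
- Listed item read literally: E_c + H_c
- Shortfall: D_c + D_s + E_s + H_s

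The shortfall is zero only if no such contacts occur. It cannot be negative, so without another source the error is always an undercount. In practice staff may treat a symptom-driven emergency visit as calcium-related, which would recover part of E_s and H_s. Nothing in the item's wording recovers D_c or D_s.

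**Step 3. Look for another route to the missing parts.**

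- Section 4.9 (Screening) and the Day of Parathyroidectomy list come too early to record later contacts.
- "Documentation of postsurgical complications" could bring symptoms to light, but it does not ask for a number of visits.
- Section 2.2.3 says that, if values are not normal at the first visit, "calcium and/or PTH is subsequently measured as necessary". This produces laboratory values, not a visit count.
- Section 5.2.3 describes entry in OnCore: "All adverse events, whether or not unexpected, and whether or not considered to be associated with the use of the study drug, will be entered". This records events, not the contacts they led to.
- Section 8.4 names office charts among the source documents, and section 8.6 retains "drug/medication history, post-surgical medical history, histopathological diagnoses of the investigated tissue samples". Both concern records that are kept. Neither tells staff to count visits, and a visit to an outside doctor may not appear in them.
- Section 8.5 ties the case report forms to the study calendar. The text contains no calendar item for doctor visits.

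None of these specifies a count of doctor visits or of contacts for associated symptoms.

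**The case against.** The strongest reply is that a list of visit procedures is not the data-collection instrument. The case report forms are not in the documents and may ask more, and charts, adverse event entries and complication notes could supply some contacts. The protocol's lists are also plainly incomplete elsewhere. The Day of Parathyroidectomy list omits the number of glands identified, the times to the first and last gland, and the intraoperative PTH behind primary outcome 2.2.1, yet nobody would conclude that these go unmeasured.

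This stands against one stronger reading. A reader might infer that doctor visits are never collected, and the documents do not show that. It does not remove the mismatch. Here the protocol does have an item for the purpose, and that item is worded more narrowly than the outcome, which is different from a list that is merely silent.

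Two further inferences do not hold. Section 2.2.3 might be read as sending abnormal patients back to a doctor between visits, but it speaks only of measuring calcium or PTH, and a blood draw need not be a doctor visit. Section 2.3.12 might be read as one pooled sum in which a single episode scores several times, but the text can equally mean separately reported counts. Collapsing episodes would conflict with an outcome defined as a number of visits. The presence of repeat surgery in the history item is no fault either, since 2.3.13 needs it.

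**Conclusion.** The outcome and its history item do not match and should be reconciled. One of three contact types and one of two reasons in 2.3.12 have no listed item, and a site working from the list alone would undercount the outcome whenever such contacts occur. This rests on a literal reading of the item and on there being no wider question in the case report forms, which are not available.

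The size of the undercount cannot be derived. A reader might apply the Background's 5–10% failure rate to the planned 160 patients and infer that 8 to 16 have unrecorded visits (160 × 0.05 = 8; 160 × 0.10 = 16). With section 6's assumed 20% attrition, 128 patients remain and the same step gives about 6 to 13 (128 × 0.05 = 6.4; 128 × 0.10 = 12.8). Neither range measures the undercount, because that rate says nothing about how often such patients see a doctor or whether the visits go unrecorded. Nor do the documents support a percentage: assuming that some share of contacts are office visits and then reporting that share as missing is circular.

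The consequence is limited. This is one of 13 secondary outcomes, and the sample size does not depend on it. It is still worth correcting, because the remedy is cheap and contacts not asked about at the time are hard to reconstruct later.

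**What to change.** In the Follow-Up Visits list and on the case report form, replace the history item with one that asks for the number and dates of doctor visits, emergency department visits and hospital admissions, whether for hypercalcemia or for symptoms associated with it, since surgery or since the last study visit. Ask it in identical words in both arms. Keep repeat surgery as a separate item serving 2.3.13.

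If the sponsor does not want doctor visits or symptom-related contacts, the alternative is to narrow 2.3.12 to the emergency department visits and admissions for high calcium that the list already covers.

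The first option costs one reworded question, a case report form line and a slightly longer interview at two existing visits, with no added visit or test. The second costs nothing in collection but gives up outpatient use as an outcome.
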